8.3 Total Analytical Error

Calculate Total Analytical Error (TAE) according to EP21 – Second Edition, Evaluation of Total Analytical Error for Quantitative Medical Laboratory Measurement Procedures. Use DOBs obtained during PRO-QC-202 – ABCA2-GIRMS Clinical Performance Measures. Calculate TAE by comparing DOB results from the original ABCA GIRMS system to DOB results from the two new ABCA2 GIRMS system.

- Determine the TAE estimate using a total of 75 patients with 8 breath samples collected for each patient (2 pre-meal samples, a 45, 90, 120, 150, 180 and 240-minute timepoints). Obtain appropriate DOB values for each patient and use these values to calculate the total analytical error.
- To calculate the TAE first calculate the difference value (d_i) by subtracting the DOB results from ABCA-A from the DOB results from the comparative method (either ABCA-C or ABCA-D).

$$d_i = \text{Candidate}_i - \frac{\sum_{j=1}^R \text{Comparative}_{i,j}}{R}$$

Where j is the replicate value from 1 to R for the ith patient (i = 1 to n)

Express d_i as a percent:

$$\%d_i = \frac{d_i}{\sum_{j=1}^R \text{Comparative}_{i,j}} * 100$$

Sort all $\%d_i$ from lowest to highest and calculate the Low and High Rank Positions to determine the TAE limits.

For 95%:

$$\text{Low Rank Position} = 0.5 + n * 0.025$$

$$\text{High Rank Position} = 0.5 + n * 0.975$$

Using these positions, find the $\%d_i$. If the rank position is nonintegral, interpolate the % difference from the values bracketing the rank position.

If the low TAE limit is greater than or equal to 30% and the high TAE limit is less than or equal to 30% then the minimum performance goal has been met.

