7.0 PROCEDURES

7.1 Validation Requirements

Determine bias and total analytical error using delta over baseline (DOB) values, i.e. differences in delta values ($\delta^{13}\text{C}$) of breath samples collected at any given timepoint and the baseline/pre-meal breath delta value) obtained by the ABCA GIRMS systems (original ABCA GIRMS and two new ABCA2 GIRMS systems. DOB values are used together with patient demographic information to calculate kPCD values. kPCD is the metric used to describe gastric emptying rates and make diagnostic decisions (refer to PRO-QC-202, ABCA2 GIRMS Clinical Performance Measures for determining diagnostic equivalence between the ABCA GIRMS instruments). DOB values are direct measures of ABCA GIRMS instruments' output (kPCDs include patient demographic information which would confound the analysis) and therefore DOBs are used to determine instrument bias/total analytical error.

PRO-CD-044, ABCA2 GIRMS Clinical Performance Measures – Patient Sample Collection, describes the collection of patient samples for clinical performance measuring studies, under an IRB approved protocol. Collect a minimum of seventy-five (75) sets of breath samples and conduct clinical performance measures experiments according to PRO-QC-202, ABCA2 GIRMS Clinical Performance Measures, by analyzing patient breath samples on the ABCA GIRMS system first and then on the ABCA2 GIRMS systems (ABCA-C or ABCA-D), then a third time on the ABCA2 GIRMS system on which the samples have not yet been analyzed.

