7.1.2 Total Analytical Error

Perform Total Analytical Error calculations according to CLSI guidance EP21 and FDA's Guidance, Assay Migration Studies for In Vitro Diagnostic Devices. Refer to section 8 for a description of the statistical analysis of the data.

Table 2. Bias and Total Analytical Error Acceptance Criteria

| Description | Justification |
|---|--|
| The Bias in DOBs on ABCA2-GIRMS should not exceed $\pm 0.5\%$ from the results from ABCA-A. | Previously approved instrument accuracy/bias requirements and manufacturer's specification for accuracy of ABCA-GIRMS. |
| Total Analytical Error in DOBs shall not exceed 30%. | Based on biologic variability data used to calculate a total allowable error (ATE) goal. |

For justification of these acceptance criteria see REP-QC-018, Validation Criteria for ABCA-GIRMS systems

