8.0 STATISTICAL ANALYSIS

8.1 Bias Comparison

Compare bias in patient samples according to EP09c – Third Edition Measurement Procedure Comparison Bias Estimation Using Patient Samples.

- Calculate the difference in DOBs, between the candidate method (ABCA-C or ABCA-D) to the comparative method (ABCA-A).
- Calculate the mean difference and the standard error (calculated by dividing the standard deviation by the square root of the number of samples) of the difference.
- Calculate the 95% confidence interval and compare results to the acceptable limit of $\pm 0.5\%$ DOBs. If the interval is within this acceptance limit the results are deemed acceptable.

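### As printed, the total analytical error pass rule can be met only if both limits equal exactly +30%, so instruments in perfect agreement fail it

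*Combined protocol and SAP*

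**What the plan says.** Exhibit C (PRO-QC-191) has two acceptance criteria, one for bias and one for TAE. Its Table 2 (section 7.1.2) gives the TAE criterion as a cap on size: "Total Analytical Error in DOBs shall not exceed 30" percent.

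Section 8.3 turns that criterion into a procedure. For each observation the ABCA-A result is subtracted from the ABCA-C or ABCA-D result, and the difference is expressed as a signed percentage. The percentages are sorted "from lowest to highest and calculate the Low and High Rank Positions to determine the TAE limits", at ranks 0.5 + 0.025n and 0.5 + 0.975n, with interpolation where a rank is not a whole number. The decision rule then reads "If the low TAE limit is greater than or equal to 30% and the high TAE limit is less than or equal to 30" percent, "then the minimum performance goal has been met".

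No place in the protocol or its exhibits gives the lower TAE bound as −30%. The other two-sided criterion in the exhibit, the bias limit, is printed with its sign as ±0.5% in Table 2 and in sections 8.1 and 8.2.

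**The concern.** The rule requires the lower of two ordered quantities to be at least 30% and the higher to be at most 30%. That leaves a single passing point instead of an interval around zero, so the rule rejects the instruments that Table 2 is meant to accept.

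Protocol section 12.5 sends the analyst to Exhibits B and C for the formulas, and section 8.3 is the only operational statement of the TAE decision. The results are to support a PMA supplement (protocol sections 4.0 and 14.0). Applied literally, the rule makes a good instrument fail. To reach the intended conclusion, the report would have to set the 8.3 rule aside in favour of Table 2 after the data are in.

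The faulty half is the lower bound, which limits how far a new instrument may read below ABCA-A. DOB feeds the kPCD value (Exhibit C, section 7.1), and a kPCD below the cut-off is classed as positive for gastroparesis (Exhibit B, section 8.1.1). An analyst who simply ignored the impossible condition would be left with no TAE limit on under-reading.

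**Working it through.** **Inputs, all from Exhibit C section 8.3 unless noted**

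- Percent difference: signed, new instrument minus ABCA-A, so perfect agreement gives 0%.
- Sort order: ascending.
- Low rank = 0.5 + 0.025n; high rank = 0.5 + 0.975n.
- Pass rule as printed: low limit ≥ 30% and high limit ≤ 30%.
- n: 75 patients, each with six post-meal DOBs. Section 8.3 does not say whether n counts patients or pooled DOBs, so both 75 and 75 × 6 = 450 were tried.
- Margin in Table 2: 30%, stated as a size.

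**Step 1: rank positions**

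- n = 75: 0.5 + 75 × 0.025 = 2.375 and 0.5 + 75 × 0.975 = 73.625.
- n = 450: 0.5 + 450 × 0.025 = 11.75 and 0.5 + 450 × 0.975 = 439.25.

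In both cases the low rank is below the high rank. With values sorted in ascending order and interpolated between neighbours, low limit ≤ high limit for any data set.

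**Step 2: the printed rule**

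Combining low ≤ high with the two printed conditions gives 30 ≤ low ≤ high ≤ 30, hence low = high = 30. On an integer grid of (low, high) pairs from −60 to +60 with low ≤ high, the only passing pair is (30, 30).

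**Step 3: constant data sets (same result at n = 75 and n = 450)**

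| All percent differences equal to | Limits | Printed rule | −30% / +30% rule |
|---|---|---|---|
| 0% (perfect agreement) | 0%, 0% | fail | pass |
| +30% | +30%, +30% | pass | pass |
| +31% | +31%, +31% | fail | fail |
| −30% | −30%, −30% | fail | pass |

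**Step 4: simulation (illustration only)**

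The documents give no SD for the percent differences. Assumed: independent normal values, mean 0, SD of 1 to 20 percentage points, 5,000 runs per setting. The entries are pass rates.

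| SD | n = 75, printed | n = 75, −30%/+30% | n = 450, printed | n = 450, −30%/+30% |
|---|---|---|---|---|
| 1 | 0% | 100% | 0% | 100% |
| 5 | 0% | 100% | 0% | 100% |
| 10 | 0% | 99.8% | 0% | 100% |
| 15 | 0% | 33.8% | 0% | 41.0% |
| 20 | 0% | 0.2% | 0% | 0% |

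The zeros follow from step 2 and do not depend on the assumed SD. The other columns show that a symmetric rule separates precise from imprecise instruments, which the printed rule cannot do.

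**Step 5: other readings of the text**

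Reversing the subtraction, or using absolute differences, still gives low ≤ high. Reading the conjunction as an alternative would pass an instrument with any low limit, however negative, provided its high limit stayed within 30%. None of these rescues the rule.

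**The case against.** The strongest objection is about the source. The whole point rests on one character, and the text was read from a PDF. Symbols are not stable in it: the same delta formula is in percent in the protocol's definitions and in permil in Exhibit B's. The ± on the bias limit survives inside mathematical markup, whereas the TAE rule is plain text. No negative number in plain text appears anywhere to show whether a leading minus would survive. This stands: a lost sign cannot be excluded, and the original page has to be looked at before this is called an error in the plan.

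The second objection is that the intent is plain. Table 2 limits the size of TAE, section 8.3 uses signed differences with separate low and high limits, and −30%/+30% is the only sensible reading. Table 2 is itself pre-specified, so a report using the symmetric rule would be following part of the plan. This also stands in part. It shows that the margin is not in doubt and the repair is easy. It does not make the printed rule usable: two pre-specified statements disagree, and the one that cannot be satisfied is the one written as the decision rule.

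Third, the pass rates under the symmetric rule depend on assumed SDs, zero mean and normality. The n = 450 runs also ignore the correlation among six DOBs that share a patient's baseline. That is correct, and the conclusion does not use those rates.

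**Conclusion.** The concern holds for the text as printed. The rule is satisfied only at limits of exactly +30% and +30%. Perfect agreement fails, and the pass rate is zero in every simulated setting. This is a matter of ordering and needs no assumption about SD, distribution or sample size. The rule contradicts Table 2 of the same exhibit.

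Because it is a decision threshold that correct instruments cannot meet, it must be fixed if the original page matches the extracted text. The error is confined to the sign of the lower bound. The 30% margin, the ranking method, the bias criterion and the diagnostic agreement criteria in Exhibit B are unaffected. The remaining uncertainty is whether the minus sign is missing from the source or was lost when the PDF was read; if it is on the original page, the point falls away.

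**What to change.** 1. Check the original page of Exhibit C section 8.3 for a minus sign before the first 30%.
2. If it is not there, restate the rule: the goal is met when the low TAE limit is at least −30% and the high TAE limit is at most +30%, assessed separately for ABCA-C and ABCA-D.

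Two small edits can be made in the same section; neither bears on the verdict.

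- The percent difference divides by the sum of the comparative replicates, although the difference itself uses their mean. Divide by the mean and state R. With R = 1, which the single ABCA-A run in Exhibit C section 7.1 implies, the result is the same; with R > 1 the printed form shrinks every percentage by a factor of R.
- The text calls the new instruments the "comparative method (either ABCA-C or ABCA-D"), whereas section 8.1 takes the difference "between the candidate method (ABCA-C or ABCA-D) to the comparative method (ABCA-A"). Use the section 8.1 labels. The order of subtraction is already right.

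The cost is a one-character correction to the rule and two editorial changes. No data, sample size or analysis step changes.

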9.0 DATA COLLECTION AND REPORTING

9.1 Collection and Review

- 9.1.1 Record all data according to SOP-QC-030, Data Generation and Review. Raw data or copies of data (marked as such with location of original data indicated) must be included in the validation package.
- 9.1.2 All data generated during execution of the validation protocol will be reviewed for completeness and accuracy in accordance with SOP-QC-030, Data Generation and Review.

9.2 Reporting

- 9.2.1 Collate the results of the executed validation protocol, including all associated data, in a verification report.
- 9.2.2 The report must be approved by the same individuals who approved the associated validation protocol(s).
- 9.2.3 Each completed validation package shall contain all relevant approved protocols, supporting data and reports.
- 9.2.4 Verification packages are controlled and archived by Document Control in accordance with SOP-QA-020, Quality Records.

10.0 NONCONFORMANCE

Document nonconformances according to SOP-QA-014, Handling and Control of Nonconformances.

12.0 REVISION HISTORY

| Revision Level | Brief Description of Revision(s) | Effective Date |
|----------------|----------------------------------|---------------------------------------|
| 00 | Initial document | Refer to first page of this procedure |

21.0 EXHIBIT D: COVID-19 TRANSMISSION MITIGATION PLAN

UNCONTROLLED COPY
Version May Not Be Current

COVID-19 TRANSMISSION MITIGATION PLAN

This COVID-19 transmission mitigation plan and questionnaire (Exhibit E) is to be utilized by Cairn Diagnostics when participating as a trial site. The sub-investigators associated with the execution of this protocol will use their COVID-19 transmission mitigation procedures.

Visit 1: Screening visit

Cairn personnel designated to participate in screening visit with the potential study participant will be required to wear a facemask and practice social distancing while in contact with the potential participant.

The potential study participant will enter the facility where they will be met by Cairn personnel and will be asked a series of questions regarding symptomology or exposure to COVID-19 (refer to Exhibit E for Study Participant Health Questionnaire). A copy of the questionnaire will be signed by the participant and Cairn personnel and will be stored in the participants file.

- If participant answers any of the questions that indicate potential symptomology or exposure to COVID-19, they will be asked to leave the facility and be advised to consult a healthcare professional. They will not be able to participate in the study at that time.
- If the participant answers the questions indicating no potential symptomology or no known exposure to COVID-19, they will meet with a qualified Cairn employee designated by the medical director and/or the medical director to give an overview explanation of the study, answer questions regarding the GEBT test procedure and provide consent to participate in the study.

Upon completion of this screening visit, the study participant will leave the facility and all PPEs worn by Cairn personnel will be disposed of in a biohazard container.

Visit 2: GEBT Administration

Cairn personnel designated to participate in GEBT administration with the study participant will be required to wear a disposable laboratory coat, gloves and facemask while in contact with the potential participant.

The study participant will enter the facility where they will be met by Cairn personnel and will be asked a series of questions regarding symptomology or exposure to COVID-19 (refer to Exhibit E for Study Participant Health Questionnaire). A copy of the questionnaire will be signed by the participant and Cairn personnel and will be stored in the participants file.

- If participant answers any of the questions that indicate potential symptomology or exposure to COVID-19, they will be asked to leave the facility and be advised to consult a healthcare professional. They will not be able to participate in the study at that time.

- If the participant answers the questions indicating no potential symptomology or no known exposure to COVID-19, they will meet with a qualified Cairn employee designated by the medical director and/or the medical director to give an overview explanation of the study, answer questions regarding the GEBT test procedure and provide consent to participate in the study.

The participant will be administered the GEBT under the supervision of Cairn's medical director via a telecommunication platform (e.g. FaceTime, Microsoft Teams, etc) by qualified Cairn personnel. The participant will remain in the area where the GEBT is being administered and will only be in contact with the qualified personnel during sample collection times.

Upon completion of the GEBT administration visit, the study participant will leave the facility and all PPEs worn by Cairn personnel will be disposed of in a biohazard container.

Visit 3: Follow up visit

Cairn personnel designated to participate in follow up contact with the participant will do so via a phone call, email, or a telecommunication platform. If the follow up is performed via a phone call or telecommunication platform, a memo noting the follow up will be placed in the participant's file.

**PRO: ABCA2 GIRMS Analytical Validation Clinical
Performance Study – Patient Sample Collection
EXHIBIT E: Study Participant Heath Questionnaire**

2 Pages

22.0 EXHIBIT E: STUDY PARTICIPANT HEALTH QUESTIONNAIRE

UNCONTROLLED COPY
Version May Not Be Current

Study Participant Health Questionnaire

In order to prevent the spread of COVID-19 (novel coronavirus) and reduce the exposure of our personnel, their families, and our visitors, we would appreciate you completing the following health questionnaire.

- 1) Do you have a fever currently or in the past 14 days? Yes No

- 2) Are you currently experiencing a cough, sore throat, shortness of breath, muscle aches/pains, or diarrhea? Yes No

- 3) Have you had contact with anyone who has confirmed, suspected, or has been tested and is awaiting results for COVID-19? Yes No

- 4) Have you been tested for COVID-19? Yes No

a. If yes, when and results: _____

Study Participant Signature

Date

Cairn Personnel Signature

Date

| | |
|--|------------------------------------|
| CAIRN DIAGNOSTICS | DOC No. PRO-CD-044.01 EXHIBIT F |
| PRO: ABCA2 GIRMS Analytical Validation Clinical Performance Study – Patient Sample Collection EXHIBIT F: Contraceptive Guidance and Collection of Pregnancy Information | Page 1 of 3 |

23.0 EXHIBIT F. CONTRACEPTIVE GUIDANCE AND COLLECTION OF PREGNANCY INFORMATION

Woman of Childbearing Potential (WOCBP)

A woman is considered fertile following menarche and until becoming post-menopausal unless permanently sterile (see below).

Women in the following categories are not considered WOCBP

1. Premenarchal
2. Premenopausal female with 1 of the following:
 - Documented hysterectomy
 - Documented bilateral salpingectomy
 - Documented bilateral oophorectomy
3. Postmenopausal female
 - A postmenopausal state is defined as no menses for 12 months without an alternative medical cause. A high follicle stimulating hormone (FSH) level in the postmenopausal range may be used to confirm a postmenopausal state in women not using hormonal contraception or hormonal replacement therapy (HRT). However, in the absence of 12 months of amenorrhea, a single FSH measurement is insufficient.
 - Females on HRT and whose menopausal status is in doubt will be required to use one of the non-estrogen hormonal highly effective contraception methods if they wish to continue their HRT during the study. Otherwise, they must discontinue HRT to allow confirmation of postmenopausal status before study enrollment.

Contraception Guidance:

Female participants

Female participants of childbearing potential are eligible to participate if they agree to use a highly effective method of contraception consistently and correctly as described in Table 1.

Table 1: Highly Effective Contraceptive Methods

| Highly Effective Contraceptive Methods That Are User Dependent^a Failure rate of <1% per year when used consistently and correctly. |
|--|
| Combined (estrogen and progestogen containing) hormonal contraception associated with inhibition of ovulation ^b 
 • Oral • Intravaginal • Transdermal |
| Progestogen only hormonal contraception associated with inhibition of ovulation 
 • Oral • Injectable |

| | |
|--|------------------------------------|
| CAIRN DIAGNOSTICS | DOC No. PRO-CD-044.00 EXHIBIT F |
| PRO: ABCA2 GIRMS Analytical Validation Clinical Performance Study – Patient Sample Collection EXHIBIT F: Contraceptive Guidance and Collection of Pregnancy Information | Page 2 of 3 |

| |
|---|
| Highly Effective Methods That Are User Independent^a |
| Implantable progestogen only hormonal contraception associated with inhibition of ovulation ^b 
 • Intrauterine device (IUD) • Intrauterine hormone-releasing system (IUS) • Bilateral tubal occlusion |
| Vasectomized partner |
| A vasectomized partner is a highly effective contraception method provided that the partner is the sole male sexual partner of the WOCBP and the absence of sperm has been confirmed. If not, an additional highly effective method of contraception should be used. |
| Sexual abstinence |
| Sexual abstinence is considered a highly effective method only if defined as refraining from heterosexual intercourse during the entire period of risk associated with the study intervention. The reliability of sexual abstinence needs to be evaluated in relation to the duration of the study and the preferred and usual lifestyle of the participant. |
| NOTES: |
| 
a) Typical use failure rates may differ from those when used consistently and correctly. Use should be consistent with local regulations regarding the use of contraceptive methods for participants participating in clinical studies.
 
b) There is no scientific reason to believe that ¹³C-Spirulina GEBT will interact with hormonal contraception and reduce the efficacy of the contraceptive method.
 |

Pregnancy Testing:

- WOCBP should only be included after a confirmed menstrual period and a negative highly sensitive urine or serum pregnancy test.
- Perform pregnancy testing with a minimum sensitivity of 25 mIU/mL on WOCBP within 48 hours prior to each Gastric Emptying Breath Test.
- Pregnancy testing will be performed whenever a menstrual cycle is missed or when pregnancy is otherwise suspected.

Collection of Pregnancy Information:

Female Participants who become pregnant

- The investigator will collect pregnancy information on any female participant who becomes pregnant while participating in this study. Information will be recorded on the appropriate form and submitted to the sponsor within 24 hours of learning of a participant's pregnancy. The participant will be followed to determine the outcome of the pregnancy. The investigator will collect follow-up information on the participant and the neonate and the information will be forwarded to the sponsor. Generally, follow-up will not be required for longer than 6 to 8 weeks beyond the estimated delivery date. Any termination of pregnancy will be reported, regardless of fetal status (presence or absence of anomalies) or indication for the procedure.
- While pregnancy itself is not considered to be an AE or SAE, and while there are not expected to be any adverse effects of ¹³C-Spirulina GEBT on a pregnancy, any pregnancy complication or elective termination of a pregnancy will be reported as an AE or SAE. A spontaneous abortion is always considered to be an SAE and will be reported as such. Any

| | |
|--|------------------------------------|
| CAIRN DIAGNOSTICS | DOC No. PRO-CD-044.00 EXHIBIT F |
| PRO: ABCA2 GIRMS Analytical Validation Clinical Performance Study – Patient Sample Collection EXHIBIT F: Contraceptive Guidance and Collection of Pregnancy Information | Page 3 of 3 |

post-study pregnancy related SAE considered reasonably related to the study intervention by the investigator will be reported to the sponsor as described in Section 8.4. While the investigator is not obligated to actively seek this information in former study participants, he or she may learn of an SAE through spontaneous reporting.

Any female participant who becomes pregnant while participating in the study will be withdrawn from the study.

UNCONTROLLED COPY
Version May Not Be Current
